13.7.2 Safety Analysis Set

The safety analysis set is defined as the population of the eligible subjects enrolled, excluding those falling under the following condition.

- Subjects who have not received any study drug

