4 STUDY DESIGN

4.1 Study Design

[figure not shown]
The design of this study is outlined in Table 4.1-1.

This study is a multicenter, intra-subject dose adjustment study. It consists of the screening period (from the time of consent to the start of study drug administration), the evaluation period (up to 24 weeks from the start of study drug administration), and the extended administration period (until Week 52 after the evaluation period).

The investigator or subinvestigator will conduct the screening after obtaining the written consent.

Subsequently, eligible subjects will be enrolled before the start of study drug administration.

Table 4.1-1. Outline of the study design

After enrollment, the date of the start of study treatment (Day 1) will be defined as Week 0, and the subjects will start to receive study drug at the starting dose of 2 mg once daily (daily dose: 2 mg). However, the starting dose may be 2 mg twice daily (daily dose: 4 mg) for subjects with a corrected serum Ca level of > 12.5 mg/dL at screening. Subsequently, the dose level will be adjusted for each subject in accordance with Section 7.1.1 "Dose, Mode of Administration, and Dosing Period" so that corrected serum Ca level can be controlled at ≤ 10.3 mg/dL, and the study drug will be orally administered at each dose level 1 to 4 times daily.

Subjects whose corrected serum Ca level have been maintained at ≤ 10.3 mg/dL for 2 weeks will be transferred to the extended administration period at the time even before Week 24. Other subjects will be transferred to the extended administration period at Week 24 if the investigator or subinvestigator has confirmed that there are no problems with their transfer to the extended administration period. See Table 9.1-1 "Schedule of observation, investigation, and examination (evaluation period)" and Table 9.1-2 "Schedule of observation, investigation, and examination (extended administration period)" for visit schedules for subjects transitioning to the extended administration period before Week 24. The study treatment period will be 52 weeks consisting of the evaluation period and the extended administration period. The time of transition to the extended administration period (starting week of prolongation) will be recorded in the electronic case report form (eCRF). Subjects will be withdrawn from the study at the end of the evaluation period if, at the discretion of the investigator or subinvestigator, they will not be transferred

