8.2 Registration Procedure

Subject registration will be carried out in accordance with the following procedures.

- 1) After obtaining informed consent, the investigator or subinvestigator will perform screening.
- 2) The investigator or subinvestigator will check subjects against all inclusion and exclusion criteria, prepare the Case Registration Form for the KHK7580 Phase 3 Clinical Study (see Attachment 3 of the protocol [supplementary volume]) for all subjects who have given their consent, whether or not the criteria are met, and notify the Study Registration Center described in Section 8.4 by fax. Registration will be done during the period from the date on which checking results for all inclusion and exclusion criteria are obtained (after screening results are known) until the start of study drug administration. However, if a subject withdraws consent or is found to be ineligible after consent has been obtained, the Case Registration Form for the KHK7580 Phase 3 Clinical Study (see Attachment 3 of the protocol [supplementary volume]) should be prepared promptly and faxed to the Study Registration Center described in Section 8.4.
- 3) The 7580-101 Study Registration Center will verify the eligibility of subjects. The 7580-101 Study Registration Center may inquire with the investigator or subinvestigator before the scheduled date of study drug administration if any questions arise about the information provided at the time of registration. For subjects who do not satisfy the inclusion criteria and/or fall under

any of the exclusion criteria, the investigator or subinvestigator will enter the reason for ineligibility, subject identifier, date of obtaining written informed consent, and sex in the eCRF.

4) The investigator or subinvestigator will record and maintain a screening log of registered subjects.

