8.3 Re-registration

Subjects who were found to be ineligible may be re-registered at the discretion of the investigator or subinvestigator, provided that consent is obtained anew and the subjects undergo screening once again. When a subject who was once found to be ineligible is re-registered, a new subject identifier will be assigned.

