9 OBSERVATION, INVESTIGATION, AND EXAMINATION ITEMS AND SCHEDULE

9.1 Schedule

Screening will be performed in subjects who have given their written informed consent. Afterwards, the study drug will be administered to subjects whose eligibility has been confirmed and for whom registration has been completed, and observation, investigation, and examination will be performed according to the schedule described in Table 9.1-1 and Table 9.1-2. Details are given in Section 9.3 “Observation and Investigation Items and the Timing Thereof” and Section 9.4 “Examination Items and the Timing Thereof.” Visits and examinations will be carried out on the scheduled visit dates with an allowable window of ± 4 days during the period between Week 2 and Week 24, and on the scheduled visit dates with an allowable window of ± 7 days thereafter. If a decision is made to discontinue study drug administration on a day of scheduled visit, the results of the examination on that scheduled visit date may be handled as the results of withdrawal examination.

Table 9.1-1. Observation, investigation, and examination schedule (evaluation period)

	Obtaining informed consent	Screening	Registration	Evaluation period														1 At discontinuation
				Time after administration of the study drug (Weeks)														
				0	2	4 ^e	6 ^e	8 ^f	10 ^f	12 ^g	14 ^g	16 ^h	18 ^h	20 ⁱ	22 ⁱ	24 ^j		
Time after administration (h)				Before administration	0.5	1	2	3										
Obtaining informed consent	X																	
Study drug administration					←												→	
Subject demographics	X ^a																	
Registration		X																
Height	X ^a																	
Body weight				X														X X
QOL assessment				X														X X
Vital sign				X				X X	X X	X X	X X	X X	X X	X X	X X	X X	X X	
Hematology				X				X X	X X	X X	X X	X X	X X	X X	X X	X X	X X	
Blood biochemistry 1	X ^b			X				X X	X X	X X	X X	X X	X X	X X	X X	X X	X X	
Blood biochemistry 2				X				X X	X X	X X	X X	X X	X X	X X	X X	X X	X X	
Urinalysis				X				X X	X X	X X	X X	X X	X X	X X	X X	X X	X X	
Plasma drug concentration ^c				X X X X	X X ^k			X ^k		X ^k		X ^k		X ^k		X ^k		
Pregnancy test ^d	X																	X
Electrocardiogram (12-lead)				X				X X	X X	X X	X X	X X	X X	X X	X X	X X	X X	
Adverse events					←												→	
Confirmation of the use status of concomitant medications	←																	→
Investigation of administration status					←												→	

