12 CRITERIA FOR SUBJECT WITHDRAWAL AND DISCONTINUATION OF THE STUDY, AND PROCEDURES THEREFOR

12.1 Withdrawal of a Subject from the Study

12.1.1 Subject Withdrawal Criteria

A subject will be withdrawn from the study if any of the following conditions apply.

- 1) The subject is found to be ineligible for participation in this study after the start of the study.
- 2) The subject wishes to withdraw the consent for the study.
- 3) It is found not feasible to conduct the necessary observations and examinations due to the subject's private reasons.
- 4) The subject experiences an adverse event, and the investigator or subinvestigator determines that the subject should be withdrawn from the study.
- 5) The subject applied PTx or parathyroid intervention therapy.
- 6) The subject has not taken investigational therapy over 8 weeks.
- 7) The investigator or subinvestigator determines that the subject should be withdrawn from the study.

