13.7 Selection of Subjects for Analysis

The following populations will be subject to analysis. Whether or not to include individual subjects in each of the analysis populations will be determined prior to database lock if necessary.

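### The safety analysis set requires subjects to be eligible as well as dosed, so a treated subject later found ineligible could be left out, with no rule for deciding

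*Combined protocol and SAP*

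**What the plan says.** Section 13.7.2 reads: "The safety analysis set is defined as the population of the eligible subjects enrolled, excluding those falling under the following condition". The single exclusion that follows is for subjects who took no study drug. The full analysis set (13.7.1) and the pharmacokinetic set (13.7.3) start from the same base of eligible enrolled subjects.

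The term eligible is not defined for these sets. Elsewhere the protocol uses it and its opposite at two different times:

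- **Before dosing.** Section 4.1 says "eligible subjects will be enrolled before the start of study drug administration". Section 8.2 says "The 7580-101 Study Registration Center will verify the eligibility of subjects" and deals with a subject who "is found to be ineligible after consent has been obtained". Section 8.3 adds: "Subjects who were found to be ineligible may be re-registered at the discretion of the investigator or subinvestigator". Under Section 9.1, "the study drug will be administered to subjects whose eligibility has been confirmed and for whom registration has been completed".
- **After the start.** Withdrawal criterion 1 in Section 12.1.1 is: "The subject is found to be ineligible for participation in this study after the start of the study". That can include a subject who has already taken drug.

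On membership of the sets, Section 13.7 says: "Whether or not to include individual subjects in each of the analysis populations will be determined prior to database lock if necessary". Section 13.6 lets the detailed analysis plan be completed as late as database lock.

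**The concern.** A safety population should be defined by exposure, because its purpose is to report what happened to everyone who took the drug. Here the definition adds a second requirement. A subject who was dosed and then found ineligible meets the exposure condition but may not count as eligible. The protocol expects that such subjects may occur and does not say how their data are analysed.

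The decision would be made subject by subject before database lock. No blinding is described, so whoever decides could already know that subject's adverse events. Setting a time for the decision does not prevent a choice made with hindsight when no criterion is given.

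Long-term safety is part of the secondary objective (Section 3.1.2) and the study is small. One subject more or less changes both the numerator and the denominator of every adverse event incidence that Section 13.1.2 calls for.

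**Working it through.** The plan gives no figure for this point, so there is none to reproduce. The check is a reading of the text, followed by arithmetic for scale.

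**What the word does in the definition.** The set is eligible AND enrolled AND dosed.

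1. Suppose eligible means judged eligible at registration. A subject judged ineligible then should not be dosed (Sections 8.2 and 9.1), and the no-drug exclusion already removes anyone undosed. The word removes nobody further.
2. Suppose eligible means eligible on all the evidence, including later findings. The word then removes a dosed subject withdrawn under criterion 1 of Section 12.1.1.
3. So the word changes membership only when it drops a subject who took the drug.

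**Does another section settle which meaning applies?**

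- Section 9.5.1 defines an adverse event for any subject receiving drug, with no eligibility condition.
- Section 13.1.2 counts events from the start of dosing, but does not say in whom.
- Section 12.1.2 requires a withdrawal examination, but says nothing about analysis sets.
- Section 17 includes early withdrawals in the Week 24 cut-off data, but does not define a population.

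None states that every dosed subject is in the safety set.

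**Scale.** The minimum of 10 treated subjects comes from Section 13.2. The sizes 15 and 20, and the single late-found ineligible subject, are assumptions for illustration. The share of exposed subjects removed is 1/n. For an event seen in one subject, the incidence 1/n becomes 0/(n−1) if the excluded subject had the event, or 1/(n−1) if not.

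| Dosed (n) | Exposed removed | All dosed kept | Excluded subject had the event | Excluded subject did not |
|---|---|---|---|---|
| 10 | 1/10 = 10.0% | 1/10 = 10.0% | 0/9 = 0% | 1/9 = 11.1% |
| 15 | 1/15 = 6.7% | 1/15 = 6.7% | 0/14 = 0% | 1/14 = 7.1% |
| 20 | 1/20 = 5.0% | 1/20 = 5.0% | 0/19 = 0% | 1/19 = 5.3% |

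Exact (Clopper-Pearson) 95% intervals at the minimum size are 0.3% to 44.5% for 1/10, 0% to 33.6% for 0/9, and 0.3% to 48.2% for 1/9. The intervals are wide and overlap heavily, so the statistical shift is small. What matters in practice is that an observed event can drop out of the table.

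**The case against.** The best defence is that eligible refers to status at enrolment. Section 13.7.2 echoes Section 4.1, where eligible subjects are enrolled before dosing. The word also has a use: Section 8.2 requires a registration form for every consenting subject, whether or not the criteria are met, so something must separate enrolled subjects from screening failures. Only one exclusion is listed, and late-found ineligibility is not it. The sentence in 13.7 can be read as fixing when membership is settled, with 13.7.1 to 13.7.3 supplying the criteria. A rule may also appear in the separate analysis plan.

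This reading is plausible and may be what the sponsor intends, but it is not written down. Screening failures are not dosed, so the no-drug exclusion already separates them and the word is not needed for that purpose. The text supplied contains no rule, and a plan completed at database lock could add one equally late.

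A second objection is that correcting 13.7.2 alone might suggest, by contrast, that late-found ineligible subjects are excluded from the full analysis set. That set and the pharmacokinetic set serve other purposes and already carry the eligibility wording, so this is no reason to leave the safety definition as it is.

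What does stand is that the consequence needs several things to coincide: a failed registration check, a dose taken, later discovery, and the less favourable reading. The documents give no rate for this.

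**Conclusion.** The concern holds, as a minor point. The wording permits a treated subject to be left out of the safety tables on grounds of eligibility, and no criterion governs the choice. At 10 treated subjects, one such exclusion removes 10% of those exposed and can turn 1/10 into 0/9. This assumes exactly one late-found ineligible subject. Its likelihood is unknown and no direction of bias is established.

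The effect is confined to the tabulated incidences. Adverse event recording (Section 9.5.4), the withdrawal examination and serious event reporting (Section 11.1.2.2.1) continue regardless. The data would exist; only their place in the tables is open.

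**What to change.** In Section 13.7.2, define the safety analysis set as all subjects who took at least one dose of study drug, regardless of eligibility. Any decision under Section 13.7 for this set would then concern only whether a dose was taken. Carry the same definition into the analysis plan before database lock.

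The cost is one wording change, with no new data or visits. If the sponsor already means eligibility as judged at registration, the change simply records that dosed subjects stay in. A sentence in 13.7 saying what eligible means for the other two sets would be a useful addition, but the safety correction does not depend on it.

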13.7.3 Pharmacokinetic Analysis Set

The pharmacokinetic analysis set is defined as the population of the eligible subjects enrolled, excluding those falling under either or both of the following conditions.

- Subjects who have not received the study drug as prescribed
- Subjects in whom no blood collection for pharmacokinetic analysis has been performed after study drug administration

14 ETHICAL CONSIDERATIONS

14.1 IRB

14.1.1 Review of the Appropriateness of Study Conduct

Prior to the conduct of the study, the protocol, the content of the informed consent form for subjects, and the appropriateness of study conduct will be reviewed from the perspective of ethical, scientific, and medical appropriateness, and approved by the IRB consulted by the head of the study site.

14.1.2 Continued Review

The investigator will submit a written summary of the current status of the study to the head of the study site at least one a year or upon request by the IRB for continued review by the IRB.

14.2 Selection of Subjects and Safety Assurance

In selecting subjects, the investigator or subinvestigator will carefully examine the appropriateness of study participation from the viewpoint of protecting human rights, by, for example, excluding those who may suffer undue disadvantage from not participating in the study (socially vulnerable persons).

The investigator or subinvestigator will determine the eligibility of subjects for registration based on the enrollment criteria and thereby avoid registration of subjects whose safety cannot be ensured.

During the study participation period, the investigator and subinvestigator will constantly monitor the health condition of subjects, such as by securing methods for emergency contact with the subjects, and collect and communicate safety information that may be relevant to the study drug. In the event of an adverse event, the investigator and subinvestigator will provide appropriate medical care, etc. to the subject, and, if necessary, discontinue study drug administration to ensure the safety of the subject.

14.3 Protection of Subjects' Personal Information and Privacy

In preparing eCRF, the investigator or subinvestigator will use subject identifiers to identify individual subjects, and protect subjects' personal information.

Persons belonging to the sponsor's organization involved in clinical studies should not divulge any subject secret learned in the course of duties in connection with the study without justifiable reason.

14.4 Time and Method of Obtaining Consent

14.4.1 Informed Consent

14.4.1.1 Informed Consent of Subjects

The investigator or subinvestigator will fully explain the details of this study to persons deemed appropriate as study subjects based on the informed consent form prescribed separately, prior to their participation in the study. In this process, a clinical study collaborator may also provide a supplementary explanation about the study. After giving the subject sufficient time to think about whether or not to participate in the study, the investigator or subinvestigator will obtain the subject's voluntary consent to participate in the study in writing (consent document defined separately) before screening.

The investigator or subinvestigator who provided the explanation and the subject will affix their names and seals or signatures onto the consent form, and the consent form will be dated by each person. If a clinical study collaborator has provided a supplementary explanation, he/she will also affix his/her name and seal or signature onto the consent form, and date it.

14.4.2 Storage of the Consent Form

The consent form will be made in triplicate unless otherwise stipulated by the study site. The investigator or subinvestigator will provide the subject with a copy of the consent form for storage and a written explanation. The investigator or subinvestigator will submit the consent form for storage at the study site to the department designated by the study site, such as the study administration office of each study site, and also store the consent form for storage by the investigator together with the medical records, etc.

14.5 Contents of the Informed Consent Form

The following items must be included in the informed consent form.

- 1) Experimental nature of the study
- 2) Study objectives
- 3) Name, title, and contact information of the investigator
- 4) Method of the study
- 5) Potential advantages to the subject's mental and physical health as a result of the use of the study drug (or, if no such advantages are expected, a statement to that effect), and potential disadvantages to the subject
- 6) Matters related to other treatment methods
- 7) Duration of participation in the study
- 8) That the subject may withdraw from the study at any point in time
- 9) That the subject will not be treated disadvantageously by not participating in or withdrawing from the study
- 10) That the source documents may be viewed by clinical research associates, auditors, IRB, etc. on condition that the subject's confidentiality is protected
- 11) That the confidentiality of the subject will be protected
- 12) Contact information of the study site in the event of health damage
- 13) That necessary treatment will be provided in the event of health damage
- 14) Matters related to compensation for health damage
- 15) The type of IRB that will investigate and deliberate on the appropriateness of the study, matters to be investigated and deliberated at each IRB, and other IRB-related matters pertaining to this study
- 16) Matters related to costs to be borne by the subject, if any
- 17) Necessary matters related to the study

The following items should not be included in the informed consent form.

- 1) A statement to the effect that a prospective subject should waive his/her rights, or any matter that makes him/her suspect such waiver

- 2) A statement to the effect that the sponsor, the study site, the investigator, or the subinvestigator is exempt from liability or their liability is reduced, or any matter that implies such exemption or reduction

14.6 Providing Information to Subjects, Revising the Informed Consent Form, and Obtaining Re-Consent

If the investigator or subinvestigator obtains new information that may influence the subject's intention to continue participating in the study, the investigator or subinvestigator will promptly explain the contents of the new information to subjects during the study, and confirm whether or not the subject intends to continue participating in the study. Then, the investigator or subinvestigator will record in the medical record the contents of the explanation, the date of the explanation, the person with whom the intention was confirmed, and the intention.

If the investigator deems it necessary to revise the informed consent form based on the explanation provided, he/she will promptly revise the informed consent form and obtain IRB approval. Then, the investigator or subinvestigator will provide an explanation once again by using the revised informed consent form, and obtain the subject's written re-consent to continue participating in the study in the same manner as when obtaining the initial consent.

15 MONETARY PAYMENT AND COMPENSATION FOR HEALTH DAMAGE

15.1 Costs Related to the Study

The cost of all tests performed during the period of KHK7580 administration should be borne by the sponsor under the system for healthcare services provided combining insurance-covered and non-covered services pertaining to the clinical study.

